163 We hypothesize that, as compared to the actual standard of care transition strategy (1:1 dose
164 conversion at the day of CSII to MDI transition), an alternative transition strategy will result in
165 lower time spent in hyperglycemia without increasing the risk for hypoglycemia. The alternative
166 strategy being (overlap transition strategy):

- 167 • Administration of insulin degludec at a 1:1 basal dose conversion dosage at day 0, with the
168 concomitant use of the insulin pump for 48 hours from transition, where CSII basal rate

169 will be reduced by 50% during the first 24 hours from transition and by 75% during 24 to
170 48 hours from transition. CSII will be disconnected after 48 hours from transition.

171 **3.2. Endpoints:**

172 Primary and secondary endpoints will be analyzed from 1-week of blinded CGM use during
173 randomization phase.

174 Primary endpoint:

175 1. Time spent in CGM glucose levels >180mg/dl

176 Secondary endpoints:

177 1. Time spent in CGM-measured “time-in-range”(glucose levels ≥ 70 mg /dl and ≤ 180 mg/dl)

178 2. Time spent in CGM-measured hypoglycemia < 70 mg/dl

179 3. Frequency of severe hypoglycemia as defined by the ADA (severe cognitive impairment
180 requiring external assistance for recovery) and severe hyperglycemia (BG \geq 250 needing
181 hospitalization)

182 4. Number of boluses (correction boluses) between groups during first 72 hours of
183 randomization

[figure not shown]
184 5. Patient-Reported Outcomes (PRO) using validated questionnaires; insulin delivery
185 satisfaction survey (IDSS) and Work Productivity and Activity Impairment Questionnaire:
186 Specific Health Problem V2.0 (WPAI: SHP) [18,19]

187 **3.3. Study design:**

188 • This is a 3-week, randomized control, open label, single center clinical trial with two study
189 arms comparing the efficacy and safety of the ‘standard of care transition’ and an ‘overlap
190 transition’ strategy

- 191 • The study consists of a screening phase, one week of run-in phase (blinded CGM
- 192 monitoring), one week of the experimental protocol following randomization phase and
- 193 one week of follow-up phase.
- 194 • Overall, the study will last 3 weeks that includes four clinical trial phases (**Figure 1**):
- 195 ○ Screening phase (Week 0): After informed consent, inclusion and exclusion, blinded CGM
- 196 will be inserted.
- 197 ○ Run-in phase (Week 0 to end of week 1): Subjects will wear blinded CGM and continue to
- 198 use CSII.

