491 **6.8. Assessments for Safety:**

492 The following safety assessments will be performed;

- 493 ▪ Time spent in CGM measured hypoglycemia (< 70 mg/dl) and time spent in hyperglycemia
- 494 (≥250 mg/dl)
- 495 ▪ AE/SAE
- 496 ▪ Documented hypoglycemic episodes
- 497 ▪ Height, weight, vitals and physical examination
- 498 ▪ Baseline laboratory assessment
- 499 ▪ Hypoglycemia unawareness assessment (using GOLD questionnaire)
- 500 ▪ Pregnancy test at screening

501 **6.9. Assessments for Efficacy:**

502 The assessment for efficacy is time spent in CGM glucose time-in-range (min/ 24 hours, 70-180
503 mg/dl) during the 7 days of randomization period.

504 **7. EVALUABILITY OF SUBJECTS:**

505 The data for a subject with minimum of 5 out of 7 days of blinded CGM prior to randomization
506 and 5 out of 7 days of blinded CGM after randomization will be evaluable and included for the
507 analysis of primary and secondary objectives.

508 **8. STATISTICAL CONSIDERATIONS:**

509 **8.1. Sample size calculation**

510 In a study by Garg and colleagues, the subjects with T1D on MDI and blinded CGM for first 4
511 weeks of the study spent average of 8.8 hours/day (~528 min/ 24 hours) in CGM defined glucose
512 above 180 mg/dl [21]. Similarly, in the recently published DIAMOND study, subjects on MDI
513 using CGM experienced average of 601 minutes (~10 hours/ day, IQR; 467-793 min) per 24 hours

514 of time spent in hyperglycemia [22]. We assume that subjects in standard of care group would
515 have more hyperglycemia than subjects in overlap transition group. Therefore, the expected CGM
516 hyperglycemia is ~ 650 minutes/24 hours in standard of care and ~ 500 minutes/24 hours in
517 overlap transition group with the differences in CGM glucose by 150 minutes/day between the
518 groups.

519 This study is powered based on the primary endpoint, which is time spent in CGM-measured
520 glucose levels >180mg/dl (hyperglycemia). We have based the sample size on minimal relevant
521 differences between the two treatment groups, using a Type I error rate of 5% and a Type II error
522 rate of 20%. We hypothesize that the primary endpoint, time in minutes spent with glucose levels
523 >180 mg/dl, will be higher in the standard treatment group than in the experimental group (overlap
524 transition group), but we will use a two-sided test to assess differences in hyperglycemia by
525 treatment group. We hypothesize a standard deviation (SD) for time spent in hyperglycemia of

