526 140 minutes (2.3 hours, or ~10% of the day) based on data from our clinic and previous
527 publications. We will have 80% power to detect a difference of 148.4 minutes (just under 2.5
528 hours) between groups, which is a clinically meaningful difference in time spent hyperglycemia,
529 with a sample size of 15 participants completing the study per group (total N=30). We have also
530 calculated the detectable difference for larger SD estimates, in case the SD in the study population
531 is larger than in our clinic in general, and for 90% power. The effect sizes detectable with a final
532 sample size of 15 patients per group at 80% and 90% power are 1.06 and 1.23, respectively, for all
533 endpoints.

534

535

536

SD	Detectable difference (minutes)	Effect size	Power
140 min	148.4 min	1.06	80%
160 min	169.6 min		80%
180 min	190.8 min		80%
140 min	171.7 min	1.23	90%
160 min	196.2 min		90%
180 min	220.8 min		90%

537

538 Detectable differences in secondary CGM endpoints, including time in range (70-180 mg/dl) and
539 time spent hypoglycemic (<70 mg/dl) have also been considered in our power analysis.

Parameter	SD	Detectable difference (minutes)	Power
Time in range (70-180 mg/dl)	160 min	169.6 min	80%
Time in range (70-180 mg/dl)	180 min	190.8 min	80%
Time in range (70-180 mg/dl)	200 min	212.0 min	80%
Time spent hypoglycemic (<70 mg/dl)	45 min	47.7 min	80%
Time spent hypoglycemic (<70 mg/dl)	60 min	63.6 min	80%
Time spent hypoglycemic (<70 mg/dl)	75 min	79.5 min	80%

540

541 8.2. Statistical Methods

542 The proposed study includes two groups, one undergoing standard treatment and the other using a
543 novel protocol of overlapping doses when transitioning from pump to MDI. Primary and
544 secondary endpoints were described earlier.

545 Study participants will be randomized using block randomization, but no stratification will be used
546 since this is a small, single center trial.

547 Our primary outcome is time spent hyperglycemic (CGM glucose values >180 mg/dl), which we
548 will compared between randomized treatment groups (standard of care vs. novel overlap protocol)

549 during the transition from pump to MDI. We hypothesize that the time spent hyperglycemic will
550 be reduced in the experimental group, using the novel overlap protocol, when compared to the
551 standard treatment group. This hypothesis will be tested using a student's t-test to compare

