552 univariate differences between the standard care group and the experimental group for each of the
553 outcomes. Secondary endpoints include time in range (70-180 mg/dl), time spent hypoglycemic
554 (<70 mg/dl), frequency of severe hypoglycemia, number of correction boluses, and patient
555 reported outcomes as defined on the page 7 of the protocol. Secondary endpoints will be
556 examined using student's t-test to compare these outcomes univariately between the standard care
557 and experimental groups. In a sensitivity analysis, CGM metrics will be evaluated in the first 72
558 hours vs entire 1 week as we expect that differences in hyperglycemia and time-in-range will be
559 more pronounced between the two groups in the first 72 hours. For both primary and secondary
560 endpoints, linear regression analysis will be used to examine outcomes by treatment group while
561 adjusting for potential residual confounders, such as age and sex, which may not be fully
562 addressed by randomization. All testing will be two-sided. The analysis will be conducted as an
563 intention-to-treat analysis.

564 **9. DATA HANDLING AND RECORD KEEPING:**

- 565 ▪ All data generated during the study will be retained by the investigator. Safety events will
566 be reported to Colorado Multiple Institutional Review Board (COMIRB) in a timely
567 manner as described under "Adverse Events".
- 568 ▪ Data management is the responsibility of the investigator. All paper and electronic data
569 will be saved in a de-identifiable manner. The data will be stored on BDC computers
570 which are secured by the University of Colorado servers. The data will be accessible only

571 by the study team and if transfer of data needed, appropriate measures, including
572 encryption of data files will be used to ensure security and subject confidentiality.

- 573 ■ The records will be stored securely and kept for minimum of 10 years per the Standards
574 Operating Procedures (SOP) of the University of Colorado [23].
575 [[http://www.ucdenver.edu/research/Research%20Administration%20Documents/COMIRB
-Policy-and-Procedures-Document.pdf](http://www.ucdenver.edu/research/Research%20Administration%20Documents/COMIRB
576 -Policy-and-Procedures-Document.pdf)]

577 **10. ETHICS:**

- 578 ■ The trial will be conducted in compliance with this protocol, ICH GCP, the University of
579 Colorado COMIRB research policy and in accordance with the Declaration of Helsinki
580 [23-25].

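### The detectable effects that section 8.1 extends to all endpoints do not usefully describe the severe-event endpoint, and the t-test assigned to it in section 8.2 is unsuitable (minor).

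*Combined protocol and SAP*

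**What the plan says.** Section 8.1 first ties power to one endpoint: "This study is powered based on the primary endpoint, which is time spent in CGM-measured" glucose above 180 mg/dl. It states an SD of "140 minutes (2.3 hours, or ~10% of the day) based on data from our clinic and previous" publications, and then: "We will have 80% power to detect a difference of 148.4 minutes (just under 2.5" hours). It goes on to generalize: the effects detectable with a final "sample size of 15 patients per group at 80% and 90% power are 1.06 and 1.23, respectively, for all" endpoints. Detectable differences in minutes are given for three CGM measures only: time above 180 mg/dl, time in range and time below 70 mg/dl.

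Section 3.2 lists, as secondary endpoint 3, "Frequency of severe hypoglycemia as defined by the ADA (severe cognitive impairment" requiring outside help), together with severe hyperglycemia needing hospitalization. No event rate or SD is given for it. Section 8.2 lists severe hypoglycemia frequency among the secondary endpoints and assigns Student's t-test to all of them, adding "All testing will be two-sided".

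**The concern.** A standardized mean difference is a natural measure for minutes per day. It is a poor one for an event that most participants will not have in one week. Section 5.2 makes events rarer still by excluding severe hypoglycemia and hospitalization for ketoacidosis in the previous three months, and hypoglycemia unawareness. Read literally, the sentence in 8.1 credits the design with a sensitivity for severe events that it has only at implausibly high risks.

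The objective covers efficacy and safety, and the hypothesis in 3.1 includes no increase in hypoglycemia risk, without a margin. What is at stake is how a result of no or very few severe events is read, and whether the planned test can be computed at all.

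**Working it through.** **Inputs.** 15 completers per group, 80% and 90% power, SD 140 min, two-sided 5% test (8.1 and 8.2). The documents give no severe-event risk, so the risks below are assumptions shown as ranges. The endpoint is taken as yes/no per participant, which is also an assumption.

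**1. The plan's own figures.** For a two-sample t-test with n per arm, the noncentrality is d·√(n/2) on 2n−2 degrees of freedom. With n=15, df=28 and the critical value is 2.048. Solving for d gives 1.0598 (80%) and 1.2264 (90%), which are the stated 1.06 and 1.23. Times 140 min, these are 148.4 and 171.7 min, as tabulated. The other tabulated differences also reproduce to rounding.

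**2. What d=1.06 means for a yes/no event.** With risk p in one arm and 0 in the other, d = p/√[p(1−p)/2] = √[2p/(1−p)], so p = d²/(2+d²) = 1.1236/3.1236 = 36%. More than a third of one arm would need a severe event within a week. At that risk the planned t-test has 85% power and Fisher's test 68%.

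**3. Which results are significant, with 0/15 in the other arm.**
- t-test, 4 vs 0: mean difference 4/15 = 0.267; variance in the arm with events (4/15)(11/15)(15/14) = 0.2095; pooled variance 0.1048; SE = √(0.1048 × 2/15) = 0.118; t = 2.256; p = 0.032. For 3 vs 0, p = 0.072.
- Fisher, 4 vs 0: 2·C(15,4)/C(30,4) = 2 × 1365/27405 = 0.0996. For 5 vs 0: 2 × 3003/142506 = 0.042.

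**4. Power against a 0% risk.** The t-test rejects when X ≥ 4 and Fisher's test when X ≥ 5, with X binomial (15, p).

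| True weekly risk vs 0% | t-test power | Fisher power |
|---|---|---|
| 5% | 0.5% | 0.06% |
| 10% | 5.6% | 1.3% |
| 20% | 35% | 16% |
| Risk needed for 80% | 34% | 41% |
| Risk needed for 90% | 39% | 46% |

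If the lower-risk arm is at 5% instead of 0%, 80% power needs 45% (t-test) or 54% (Fisher).

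**5. No events.** The t statistic is then 0/0. If both arms share a weekly risk of 1%, 2% or 5%, the chance of no event in 30 participants is 0.99³⁰ = 74%, 0.98³⁰ = 55% or 0.95³⁰ = 21%. The exact two-sided 95% upper limit for 0/15 is 1 − 0.025^(1/15) = 21.8%.

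**6. Error rate of the t-test.** Given four events in all, a 4–0 split in either direction has probability 0.0996 when the arms do not differ, and the t-test calls it p=0.032. Averaged over event counts the picture differs. At a common risk of 5% the main term is 2 × P(X≥4) × P(Y=0) = 2 × 0.0055 × 0.463 = 0.5%; at 10% it is 2 × 0.0556 × 0.206 = 2.3%. The t-test is thus anti-conservative at that small event count, but its overall rejection rate stays below 5% at these risks.

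**The case against.** The best defense is that section 8.1 rests power on the primary endpoint alone, and that an effect above one SD openly signals low sensitivity. The numbers are right, and under the t-test that the plan names, d=1.06 still carries nominal power above 80% on yes/no data. All of this stands: the fault is one of scope and choice of test, not of arithmetic. It does not rescue the sentence, because the effect in question is about 36% against 0% in a week.

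Hypoglycemia is also assessed as a continuous measure. Section 6.8 lists CGM time below 70 mg/dl as a safety assessment, and 8.1 gives it detectable differences of 47.7, 63.6 and 79.5 min for SDs of 45, 60 and 75 min. The safety question therefore does not rest on severe-event counts alone.

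Three stronger readings are not supported:
- A reader might infer that the plan claims adequate power for safety. No section says so; a powered null on severe events would be a misreading that the phrase permits.
- A reader might infer that the figures also fail for questionnaire scores such as the "satisfaction survey (IDSS) and Work Productivity and Activity Impairment Questionnaire". The sentence is conditional on 15 per group, and the documents do not say that any score will be available in fewer.
- A reader might infer that the t-test inflates the overall false-positive rate for rare events. Step 6 shows that it does not at low risks; the trouble is its p-value at particular small counts, and its failure when there are none.

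**Conclusion.** The point holds as a minor one. The wording in 8.1 is too broad: 1.06 and 1.23 are sound for continuous endpoints with 15 values per arm and uninformative for severe events, where a true weekly risk of 10% against 0% would be detected 5.6% of the time with the planned test and 1.3% with an exact one. The t-test in 8.2 is a poor choice for this endpoint whatever the wording of 8.1.

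The size rests on reading the endpoint as yes/no per participant, on 15 evaluable per arm, and on assumed risks. The conclusion is the same across the whole range shown. The concern about how a null would be reported is an inference, not something the plan states.

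**What to change.** In section 8.1, limit the statement to continuous endpoints observed in 15 participants per group, and add that the trial is not powered for severe hypoglycemia or severe hyperglycemia (0/15 is compatible with a weekly risk of up to 21.8%).

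In section 8.2, remove severe-event frequency from the t-test list. Report the number of participants with an event per arm with exact 95% intervals, and use Fisher's exact test if a comparison is made. Both sections must change together; editing 8.1 alone would contradict 8.2.

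Name all randomized participants as the denominator. Section 7 restricts secondary objectives to participants with at least 5 of 7 CGM days after randomization, and section 5.3 lists severe episodes as a reason for withdrawal. A participant with an event could otherwise drop out of the endpoint that counts it. This also agrees with the intention-to-treat statement in 8.2.

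The cost is a few sentences in two sections. Sample size, primary analysis and data collection do not change.

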234 2) Patients with T1D diagnosed for at least 12 months

235 3) Point-of-care HbA1c levels between $\geq 6.5\%$ and $\leq 8.5\%$

236 4) Patients on CSII (any insulin pump) for at least past 6 months

237 5) Willing and able to wear a blinded CGM during the time of study period

238 6) Willing to perform self-monitoring of blood glucose (SMBG) at least 4 times a day

239 7) Ability to provide informed consent before any trial-related activities

240 8) Not willing to or plan any travel out of Colorado during the 3 weeks of study period

241 9) Willing to use insulin degludec in the morning once a day

242 **5.2. Exclusion criteria**

243

244 1) Age < 18 years and > 65 years

245 2) HbA1c $> 8.5\%$ at screening

246 3) Less than 12 months of insulin treatment

247 4) Patients on 670G or Tandem Control IQ (Medtronic and Tandem Hybrid Closed-loop
248 systems) and not willing use manual mode during the study period

249 5) Patients with T1D using any glucose lowering medications other than insulin

250 6) Pregnancy, breast feeding, and positive pregnancy test during screening

- 251 7) Women of childbearing age wanting to become pregnant or not using adequate
252 contraceptive measures
- 253 8) Current or recent (< 2 weeks prior to visit 1) use of any steroidal medication, or anticipated
254 steroidal treatment, during the study period
- 255 9) eGFR below 45 ml/min/1.73 m² using MDRD formula
- 256 10) History of severe hypoglycemia in the previous 3 months
- 257 11) History of diabetic ketoacidosis (DKA) requiring hospitalization in the past 3 months
- 258 12) History of allergy to any form of insulin or its excipients
- 259 13) History of allergy to adhesives
- 260 14) Unwilling to use blinded CGM during the study period
- 261 15) Unwilling to perform SMPG at least 4 times a day
- 262 16) Known history of alcohol abuse or illicit drug use within 6 months prior to screening
- 263 17) Use of investigational drugs within 5 half-lives prior to screening
- 264 18) Participation to other study trials during the study period
- 265 19) Elevated liver enzymes (AST and ALT) 3 times the upper limit of normal
- 266 20) Hypoglycemia unawareness defined as GOLD score ≥ 4 [20]
- 267 21) Any comorbidities or medical conditions that make a person unfit for the study at the
268 discretion of the investigators
- 269 22) Anticipated travel across different time zones (difference greater than 4 hours) or

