789 several weeks. The risk of an infection is less than 1 in 1,000 people.

790 c) Related to CGM

791 Wearing sensors can cause adverse skin reactions such as pain at the site sensor insertion. The
792 adhesive pads may cause skin erythema for 1 to 2 days or more. An allergic reaction to 1 or more
793 parts of CGM devices may occur which can be mild, moderate, or severe (rare). In rare cases, an
794 infection at the sensor site may occur. In rare cases, the sensor or needle may break inside the body
795 and would require a minor surgical procedure to remove it. We will also screen out individuals
796 with a history of serious skin reactions to adhesives.

797 d) Risk of Hypoglycemia (Low Blood Sugar)

798 As with any person with diabetes who uses insulin, there is always a risk of having low blood
799 sugar (hypoglycemia). Symptoms of low blood sugar can include sweating, jitteriness, and not
800 feeling well. There is also the possibility of fainting or seizures (convulsions), brain damage, or
801 death with a very low blood sugar. Since we will be closely monitoring participants during this
802 study, a serious low blood sugar is less likely to occur in any study participant. Even if a low blood
803 sugar does occur, it usually goes away quickly with treatment (carbohydrates) that raises the blood
804 sugar. A severe low blood sugar may require that a participant get an injection of glucagon and/or
805 have emergency services to help raise his/her blood glucose level.

806 e) Risk of Hyperglycemia (High Blood Sugar)

807 Hyperglycemia usually does not cause many obvious symptoms, but participants may become
808 thirsty, fatigued, or have a higher level of sugar in their urine. In severe cases of hyperglycemia,
809 diabetic ketoacidosis (DKA) or coma may occur. Hyperglycemia leading to DKA can lead to renal
810 failure (kidney failure), cardiac arrhythmia (irregular heartbeat), myocardial infarction (heart
811 attack), rhabdomyolysis (muscle breakdown), and even death. A serious effect from

812 hyperglycemia is not expected to occur in any study participant, as we will be monitoring blood
813 glucose levels frequently.

814 f) Psychosocial Questionnaires

815 Answering questionnaires about thoughts, concerns, and distress related to diabetes and general
816 quality of life assessments may result in undesired thought processes and/or emotions. These
817 feelings may be transitory, recurrent, or permanent though most risks are minimal/transitory.

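### Section 8.2 sets Student's t-test for severe hypoglycemia and severe hyperglycemia, where the likeliest result (no events in either arm) leaves the test undefined

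*Combined protocol and SAP*

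**What the plan says.** Section 3.2 lists as secondary endpoint 3 "Frequency of severe hypoglycemia as defined by the ADA (severe cognitive impairment" needing outside help), together with severe hyperglycemia, defined as a glucose of at least 250 that leads to hospitalization.

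Section 8.2 lists among the secondary endpoints time in range, time below 70 mg/dl and then "<70 mg/dl), frequency of severe hypoglycemia, number of correction boluses, and patient" reported outcomes. It states that all of them will be "examined using student's t-test to compare these outcomes univariately between the standard care" and experimental groups. Severe hyperglycemia is not named in that list. It falls under the rule because section 8.2 refers back to the endpoints already described, including the page 7 definitions.

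The only other model is a linear regression for primary and secondary endpoints, adjusted for covariates such as age and sex. Section 8.2 has no exact, rank-based or transformed analysis and no rule for an endpoint with zero events.

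Section 8.1 plans for 15 completers per group. For time below 70 mg/dl it gives SDs of 45, 60 and 75 minutes, but no mean and no distribution.

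**The concern.** Severe events are yes/no occurrences, and the protocol selects against them. Section 5.2 excludes patients with a "History of severe hypoglycemia in the previous 3 months", with hospitalized ketoacidosis in the same period, or with a GOLD score of 4 or more. Section 14.2 describes serious low blood sugar as less likely under the study's monitoring and does not expect serious effects of hyperglycemia. The randomized period lasts one week.

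A test that compares means using a pooled variance needs some variation in the data. If no patient has an event there is none, and the planned analysis returns nothing. If a handful of patients have events, the t reference distribution is a poor approximation for a 2 × 2 table.

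The study hypothesis in section 3.1 is less hyperglycemia without more hypoglycemia. Severe hypoglycemia is part of the evidence for the second half of that claim, so it should have a prespecified analysis that works for the data most likely to arise.

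**Working it through.** **The plan's own figures.** Two-sample t-test power from the noncentral t distribution, with n = 15 per arm and two-sided 5%, gives a detectable standardized difference of 1.0598 at 80% power and 1.2264 at 90%. The plan's rounded 1.06 gives 1.06 × 140 = 148.4 min for the primary endpoint, and 1.06 × 45 = 47.7, 1.06 × 60 = 63.6 and 1.06 × 75 = 79.5 min for time below 70 mg/dl. These match section 8.1, so the sample size is not in question.

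**Chance of no severe event.** The documents state no rate, so the per-patient rate p over the week is an assumption. The chance that none of 30 patients has an event is (1 − p)^30.

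| Assumed p | No event in 30 | At least 4 events in 30 |
|---|---|---|
| 0.5% | 86% | 0.002% |
| 1% | 74% | 0.02% |
| 2% | 55% | 0.3% |
| 5% | 21% | 6% |

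**The test at zero events.** Both means are 0 and the pooled variance is 0, so t = 0/0. The linear regression fails in the same way, because a constant outcome leaves zero residual variance and zero standard errors.

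**The test in sparse tables.** For 4/15 against 0/15:
- The difference in proportions is 4/15 = 0.2667.
- The pooled variance is 15 × 0.2667 × 0.7333 / 28 = 0.1048.
- The standard error is √(0.1048 × 2/15) = 0.1182.
- t = 0.2667/0.1182 = 2.26 on 28 df, p = 0.032.
- Fisher's two-sided p = 2 × C(15,4)/C(30,4) = 2 × 1365/27405 = 0.100.

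| Events, one arm against none | t-test p | Fisher p |
|---|---|---|
| 0 | undefined | 1.00 |
| 3 | 0.072 | 0.224 |
| 4 | 0.032 | 0.100 |
| 5 | 0.013 | 0.042 |

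**What an exact interval adds.** For 0/15 the two-sided 95% upper limit is 1 − 0.025^(1/15) = 21.8%. An arm with no events is therefore still compatible with a risk of about one in five.

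**Overall error rate.** Enumerating all 16 × 16 outcomes of two Binomial(15, p) arms, the t-test's type I error is 0.002% at p = 1%, 0.03% at 2% and 0.5% at 5%. Its maximum over all rates is 5.5%, near p = 28%.

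**Time below 70 mg/dl.** These results come from simulation with 15 per arm, the plan's SDs and assumed means of 40, 60 and 80 min. The t-test's type I error is 3.0% to 4.9%. Power for a halving from mean 60, SD 60 depends on the assumed shape:

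| Assumed shape | t-test | Wilcoxon |
|---|---|---|
| Lognormal | 46% | 55% |
| Gamma | 39% | 34% |
| Lognormal with 20% zeros | 29% | 26% |

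**Correction boluses.** For Poisson or overdispersed counts with assumed means of 3 to 10, the t-test's type I error is 4.5% to 5.1%.

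**The case against.** The best defence is that the zero-event case hardly matters. If nobody has an event, Fisher's p-value is 1.00 and any report would show zero and zero. Severe events are also captured outside the t-test, through AE/SAE reporting, the two phone calls after randomization and monthly review by an independent safety officer. It is true that no test is informative at zero events. But those processes do not supply a prespecified comparison for a named secondary endpoint, and the exact interval does convey something that a bare pair of zeros does not.

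The defence is also right on several stronger conclusions that a reader might draw, none of which the documents support.

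- **That the t-test is too liberal for rare events.** It is not at the rates one would expect here; its overall error is far below 5%. The 4-against-0 table illustrates how the p-values can diverge, but at least four events in 30 patients has a probability of only 0.02% at a 1% rate and 6% at 5%.
- **That the t-test hides harm in severe events.** Fisher's test is the less sensitive of the two. At assumed true rates of 1% and 20%, power is 31% for the t-test and 14% for Fisher's test.
- **That the t-test loses power for time below 70 mg/dl.** The outcome is bounded at zero and skew is plausible, but the plan gives no mean or shape, and the ranking of the tests reverses between plausible shapes.
- **That correction boluses need a count model.** The t-test holds its error rate there.

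**Conclusion.** The point holds for severe hypoglycemia and severe hyperglycemia. Section 8.2 prescribes a test that cannot be computed in the likeliest outcome: no events has a probability of 55% to 86% at assumed per-patient rates of 2% down to 0.5%. At 5% that probability falls to 21%. The rates are assumptions, but the direction follows from the protocol's own exclusions and its statements about expected risk. That the test is undefined at zero events does not depend on any rate.

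For time below 70 mg/dl the t-test is a defensible choice, and section 8.1 plans that endpoint as a difference in mean minutes. Neither test is uniformly better, so this part supports at most an added sensitivity analysis. This is a gap in the analysis of one secondary safety endpoint and does not touch the primary result.

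**What to change.** In section 8.2, take severe hypoglycemia and severe hyperglycemia out of the t-test and regression sentences. For each, report the number of events and the number of patients with at least one event per arm, with exact 95% confidence intervals and Fisher's exact test.

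State that this analysis includes all randomized patients. Section 5.3 withdraws participants with severe episodes, and section 7 limits the analysis of secondary objectives to patients with at least 5 of 7 CGM days after randomization. A patient with an event could therefore fall out of the evaluable set, although section 8.2 calls the analysis intention-to-treat.

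For time below 70 mg/dl, keep the mean difference and t-test, and optionally add a rank-based or transformed sensitivity analysis. Leave the t-test for time in range and correction boluses.

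The cost is a few sentences and no new data. The downside is that Fisher's test is conservative, so the exact intervals should carry the interpretation: a non-significant p-value, or no events at all, should not be read as evidence of equal risk.
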